3. STUDY DESIGN

The study is performed in the cardiology clinics of a tertiary care training hospital. The study is approved by the local ethics committee (number 2023/0129 on 22/02/2023).

Study Population:

The study population consists of premenopausal women who applied to the outpatient clinic with chest pain between February 2023 and July 2023. Patients report that they have a regular menstrual cycle.

Written informed consent is obtained from the patients.

All patients have transthoracic echocardiography. Echocardiography demonstrates normal left ventricular systolic and diastolic function. Echocardiography does not show wall motion abnormality or significant valvular heart disease.

All patients are evaluated for cardiovascular risk. Risk factors such as hypertension, diabetes mellitus, cigarette smoking, hyperlipidemia, family history of CAD, and drug use are questioned (16). Cardiovascular risk factors are defined as follows. Hypertension is defined as a persistent elevation in office systolic BP ≥ 140 and/or diastolic BP ≥ 90 mmHg, or a 24-hr ambulatory BP monitor average of $\geq 130/80$, or requirement of chronic use of antihypertensives. Hyperlipidemia is defined as elevated total cholesterol (>240 mg/dl), low-density lipoprotein cholesterol (LDL-C) (>160 mg /dl), triglycerides > 150 mg/dl, high-density lipoprotein cholesterol (HDL-C) (< 50 mg /dl). Cigarette smoker is defined as having smoked at least 100 cigarettes in lifetime. Type 2 diabetes mellitus is defined as fasting plasma glucose (FPG) ≥ 126 mg/dL, or 2-hour plasma glucose ≥ 200 mg/dL during a 75-g oral glucose tolerance test (OGTT), or random plasma glucose ≥ 200 mg/dL in a patient with classic symptoms of hyperglycemia, or hemoglobin A1c (HbA1c) $\geq 6.5\%$ (48 mmol/mol). Self-reported family history of premature CAD is defined as having a first-degree relative with premature CAD (men, age <55 years; women, age <65 years).

Menstrual cycle

The history of the menstrual cycle of the patient is obtained in detail. The duration and regularity of the menstrual cycle, the amount of bleeding, and the number of days the bleeding lasted are noted for each patient. Patients with irregular menstrual cycles, breakthrough bleeding, spotting, gynecological examination, or treatment plan that would disrupt the menstrual cycle are excluded from the study.

The early and late follicular phases are determined from the history. The early follicular phase ETT is planned on the 3rd day of menstrual bleeding, while the menstrual bleeding continues. The late follicular phase ETT is planned on the 3rd day after the menstrual bleeding ends. Hormone levels are measured before each ETT to ascertain the phase of the menstrual cycle. Two ETTs are performed on each participant.

The blood sample is taken 30 minutes before the ETT to measure follicular stimulating hormone (FSH), luteinizing hormone (LH), estrogen, progesterone, and hs-cTn. After the test, the patient is allowed to rest for 15 minutes and blood is taken to check the 2nd hs-cTn after ETT.

Sampling Method: Probability Sample

Minimum Age: 20 years

Maximum Age: 55 years

Sex: Female

Gender Based: Yes

Female patients in the pre-menopausal period

The inclusion criteria are:

1. Premenopausal female patients with regular menstrual cycles,
2. ages between 20-55,
3. Patients have been seen in the cardiology clinic by a cardiologist for the symptoms of chest pain with a clinical suspicion of angina or angina equivalent.
4. A cardiologist has ordered ETT as a diagnostic test for the symptoms of chest independent of the study protocol
5. Patients can understand and sign the informed consent.

[figure not shown]
The exclusion criteria are:

1. Women with menopause or menopause-related symptoms or menstrual cycle irregularity or use of hormonal therapy or oral contraceptives, current pregnancy
2. patients with a history of CAD,
3. secondary or uncontrolled hypertension,
4. history of valvular heart disease,
5. left ventricular hypertrophy on echocardiography,
6. abnormal systolic or diastolic function or wall motion abnormality on echocardiography,
7. history of cardiac arrhythmia or heart failure, pericarditis or myocarditis
8. history of cancer, stage ≥ 3 kidney failure, liver failure, history of psychiatric illness, history of, recent infection.
9. pre-existing ECG abnormality that would confound the interpretation during the ETT (baseline ECG was considered abnormal in the presence of the following findings: prolonged QT interval, chamber hypertrophy, alterations in the ST-T waves, any degree of heart block, T-wave abnormalities, premature ventricular contractions (PVCs), right bundle branch block (RBBB), left bundle branch block (LBBB), left or right axis deviation, or any abnormal rhythm other than normal sinus rhythm).
10. patients who cannot tolerate Bruce protocol in the first ETT
11. lack of ability or mental capacity to understand the study

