1. OBJECTIVE AND HYPOTHESES

Objective: To compare exercise treadmill test (ETT) results in premenopausal women at the early and late follicular phases of the menstrual cycle.

General Hypothesis:

False positive results are commonly observed in women after exercise treadmill test (ETT). The studies report severe variability in the sensitivity and specificity of ETT in detecting significant coronary artery disease (CAD). Sensitivity ranges from 23% to 100% and specificity ranges from 17% to 100% (1, 2). ETT utilizes electrocardiography (ECG) along with heart rate (HR) and blood pressure (BP) monitoring during exercise, typically involving a treadmill. The major finding of ETT is the ST segment deviation from the baseline. False positive stress ECGs are common especially in premenopausal women, limiting the specificity of the test (3-6).

Menstrual periods can cause biological variability in ETT in premenopausal women (7). The menstrual period is divided into phases: early follicular (days 1-5), late follicular (days 6-12), ovulation (days 13-15), early luteal (days 16-19), mid-luteal (days 20-23) and late luteal phases (24-28 days). Early follicular phase is characterized by low estrogen and low progesterone, late follicular phase is characterized by low progesterone and high estrogen. Mid-luteal phase is characterized by high progesterone and high estrogen levels (7-9). Early and late follicular phases of the menstrual cycle in women demonstrate nearly 4 fold differences in estrogen levels. The menstrual period phase affects thermoregulation and physical working capacity in women (9, 10). Estrogen has protective and vasodilatory effects on the cardiovascular system (11). With the discovery of high sensitive cardiac troponins (hs-cTn), minute changes of hs-cTn have become detectable (12).

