The effects of menstrual periodic changes on the results of exercise treadmill test in premenopausal women have not been clearly defined. Primary purpose of the study is to investigate the biological causes of false positive test results in the treadmill exercise test in premenopausal women. Estrogen is known to have direct vasodilatory effects on coronary arteries. Early and late follicular phases of the menstrual cycle are characterized by low and high estrogen levels, respectively. The Early Follicular Phase starts on the first day of the menstrual cycle and ends when oestradiol begins to increase. It is characterised by increasing LH and FSH and constant low levels of oestradiol. The late follicular phase starts with the increase in oestradiol and ends at its preovulatory peak (7-10). False positive stress ECGs are commonly reported especially in premenopausal women, limiting the specificity of the ETT (3-5). Studies demonstrated that HR adjustment of in exercise-induced ST segment depression using the ST/HR slope or ST/HR index could improve the sensitivity and specificity of ETT (2, 13-15).

The hypothesis of the study is that ETT results and hs-cTnT release after ETT will change at the early and late follicular phases in premenstrual women.

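### Does the plan need a hormone criterion for cycle phase, and a rule for pairs whose hormones disagree with the calendar?

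*Protocol*

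**What the plan says.** Section 3 of the protocol (Menstrual cycle) gives two statements about phase. It is assigned by history: "The early and late follicular phases are determined from the history". It is also to be checked by assay: "Hormone levels are measured before each ETT to ascertain the phase of the menstrual cycle". The early test is set for the third day of bleeding, while bleeding continues. For the other test, "The late follicular phase ETT is planned on the 3rd day after the menstrual bleeding ends".

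Section 1 describes the phases in two ways. One is by calendar: "early follicular (days 1-5), late follicular (days 6-12), ovulation (days 13-15". The other is by physiology: "The late follicular phase starts with the increase in oestradiol and ends at its preovulatory peak". It adds the size of contrast to expect: "Early and late follicular phases of the menstrual cycle in women demonstrate nearly 4 fold differences in estrogen levels". These statements are background; none is written as a limit that a sample must meet.

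The SAP lists estrogen, progesterone, FSH and LH by phase as a secondary endpoint. For numerical data it plans a paired t-test and/or Wilcoxon test. Its null hypothesis is that the ST/HR index does not differ between menstrual phases. It plans 34 patients for an effect size of 0.5, with 5% type I error and 80% power.

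**The concern.** The assay is given a job, and no rule lets it do that job. A woman may be tested on the scheduled late day before her estrogen has risen. The visible text does not say whether her pair is kept, repeated or removed. Two figures, including the study flow, are not reproduced in the text available for review, so a rule could sit there.

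The stated aim sharpens the point: "Primary purpose of the study is to investigate the biological causes of false positive test results in the treadmill exercise test". If the ST/HR result is null, a reader will ask whether estrogen has no effect or whether some women had no estrogen contrast. A significant average rise in estrogen does not fully answer that, because it can coexist with many pairs that did not rise. If the result is positive, no planned analysis ties it to estrogen. Silence on discordant pairs might also seem to leave room to drop them after the ST/HR data are known.

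**Working it through.** **1. The plan's own figure.** Inputs from the SAP: effect size 0.5 (mean paired difference divided by its SD), two-sided 5%, power 80%. For a paired t-test with n = 34, the noncentrality is 0.5 × √34 = 2.92 on 33 degrees of freedom, and power is 80.8%. With n = 33 it is 79.5%. The stated 34 is reproduced.

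**2. Does the schedule reach the intended phase?** For bleeding of L days, the late test falls on cycle day L + 3. The early test requires bleeding to continue on day 3, so L is at least 3.
- L = 3 gives day 6.
- L = 9 gives day 12.
- L = 10 gives day 13, the first day outside the range.

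The bleeding rule therefore lands in the protocol's days 6–12 for L = 3 to 9. Section 3 also excludes "Patients with irregular menstrual cycles, breakthrough bleeding, spotting", and the exclusion list removes women with menopausal symptoms or on hormonal therapy or oral contraceptives.

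**3. What happens to a discordant pair under the text as written?** Phase comes from history. No exclusion criterion refers to a hormone value, and the SAP defines no hormone-based analysis set. Followed literally, the pair stays in.

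**4. What could be lost?** The documents give no share p of women without an estrogen rise, so p is assumed. Suppose 0.5 is the effect in women who rise, and the others have a fraction r of it. The mean is 0.5(1 − p) + 0.5rp and the variance is 1 + p(1 − p)[0.5(1 − r)]². For p = 10% and r = 0, the mean is 0.45 and the variance 1 + 0.09 × 0.25 = 1.0225, so the effect size is 0.45/√1.0225 = 0.445 and power is 71%.

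| Assumed p | Power at 34 pairs, r = 0 | Power at 34 pairs, r = 0.5 |
|---|---|---|
| 10% | 71% | 76% |
| 20% | 60% | 72% |
| 30% | 49% | 67% |
| 40% | 38% | 61% |

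These losses arise only if 0.5 is taken to apply to risers alone. The SAP states 0.5 for the difference between phases in the women enrolled. On that reading any non-risers are already inside the 0.5, and power stays at 80.8%.

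**5. Would hormone-based analyses repair an ambiguous null?** This was simulated with 34 pairs. Assumptions: a fourfold estrogen ratio in risers and none in the rest, SD of the log ratio 0.5 to 1.0, and a ratio of 2 purely as an example of a confirmed set.

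- *All-or-none effect.* At p = 10%, confirmed-set power is 61–71%, against 71% in all women. At p = 40% it is 38–50%, against 38%. Regression of ST/HR change on log estrogen change has power of 6–9% and 11–19%.
- *Effect exactly proportional to the log ratio, no assay error.* At p = 10%, confirmed-set power is 76–82%, against 66–70% in all women. At p = 40% it is 58–68%, against 34–37%. Regression power is 26–58% and 39–67%.

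The example ratio would also discard 8–24% of true risers. A simple correlation in 34 pairs reaches 80% power only for |r| of about 0.47.

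**The case for a change.** The strongest counter-argument concerns interpretation, not validity. At an assumed 40% of non-risers, the group estrogen test was still significant in at least 96% of simulated trials, and 60–63% of trials combined a significant estrogen rise with a null ST/HR result. A group-level check can therefore pass while many pairs lack the contrast. The blood is drawn anyway, so a pair-level check would cost only a few lines of SAP text.

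Part of this stands. Only a wholly absent contrast is sure to show in the planned hormone comparison; a partial shortfall could stay hidden there. The phrase about ascertaining phase is loose beside the statement that phase comes from history.

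The rest is weaker than it looks. Because the estrogen test is almost always significant, the joint figure is nearly one minus the ST/HR power: 100 − 38 = 62%. It restates type II error under an assumed 40% share and an assumed absence of effect in that subgroup. The objective, the hypothesis and the SAP's null all concern phase, and the background also cites phase effects on thermoregulation and working capacity. No endpoint turns the broad aim about biological causes into a claim about estrogen dose. Dropping pairs after seeing ST/HR data would depart from the text; nothing in the text permits it. Individual hormone values are collected, so an analyst can still report how many pairs show the expected rise.

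**Conclusion.** No change to the plan follows. The paired comparison by scheduled phase is valid for the stated null, and the sample size of 34 is correct on its own inputs (80.8% power). The calendar timing agrees with the protocol's phase days for bleeding of 3 to 9 days. Read literally, discordant pairs remain in the analysis.

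What is missing is detail: an operational hormone check and an explicit sentence on discordant pairs. Analysts can supply both sensibly by analysing all scheduled pairs and describing the hormone values alongside. A confirmed-set analysis or a regression on estrogen would be a supportive addition that cannot alter the primary conclusion. Under an all-or-none effect with 10% non-risers, it would do no better than the planned test; clear gains need an effect proportional to estrogen and an error-free assay.

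This conclusion rests on reading 0.5 as the effect in all enrolled women, and on the two unseen figures containing no contrary rule. Every power loss quoted depends on an assumed share of non-risers that the documents do not give.

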4. STUDY SCHEDULE

Assessment	Screening visit-(Day 0)	Recruitment	First ETT	Phone visit on day 7 after ETT (± 2 days)	Second ETT at a different menstrual phase	Phone visit on day 7 after ETT (± 2 days)
Informed Consent Form	X	X	X		X	
Demographic characteristics	X					
Blood pressure, heart rate, and other vital signs	X	X	X	X (by phone)	X	X (by phone)
History/ Physical examination	X	X	X		X	
Hs-cTn and hormone laboratory workup			X		X	
Inclusion/exclusion criteria	X					
Pregnancy test (serum / urine)	X					

5. THE STUDY FLOW is demonstrated below.

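### The readable text lets either menstrual phase be tested first and the planned paired test has no test-order term, so any repeat-test effect would shift the phase difference in proportion to order imbalance

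*Protocol*

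**What the plan says.** Each woman has two treadmill tests (ETTs). Protocol section 3 (Menstrual cycle) gives the days: "The early follicular phase ETT is planned on the 3rd day of menstrual bleeding, while the menstrual bleeding continues" and "The late follicular phase ETT is planned on the 3rd day after the menstrual bleeding ends". Neither sentence says which test comes first or whether both fall in one cycle. Protocol section 4 (Study schedule) has a column for a first ETT and one for a "Second ETT at a different menstrual phase", with a telephone contact between them. Section 5 refers to a study-flow figure that is not available in the text, and another figure is missing from section 3.

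The design is an observational case-crossover. Under the inclusion criteria, "A cardiologist has ordered ETT as a diagnostic test" independently of the study, so clinical scheduling can influence which phase is tested first. Exclusion criterion 10 removes "patients who cannot tolerate Bruce protocol in the first ETT".

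The SAP (The statistical tests) compares numerical data between phases with a paired t-test or Wilcoxon test, according to distribution, at two-sided 5%. It names no term for test order and no analysis by order. The sample size is 34 women, for 80% power at an effect size of 0.5.

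**The concern.** The within-woman contrast is the study's only control. It removes stable differences between women, but not a difference between a first and a second test. Familiarity with the treadmill, for example, could alter the second result whatever the phase. A paired test cannot tell such an effect from a phase effect unless the starting phase is balanced or order is in the analysis.

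The shift can go either way. If most women start in the early phase, the repeat-test effect is added to the late-minus-early difference; if most start in the late phase, it is subtracted. A phase effect in the ST/HR index could therefore be created or hidden.

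**Working it through.** **Inputs.** From the SAP: n = 34, paired, two-sided alpha 5%, power 80%, effect size 0.5, read as the mean paired difference divided by the SD of the paired differences. The repeat-test effect and the order split are not in the documents; both are assumed and shown as ranges.

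**The plan's own figure.** Noncentral t, 33 df, noncentrality 0.5 x sqrt(34): power 0.808. With 33 women it is 0.795. The stated 34 reproduces.

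**Size of the shift.** Let D = late minus early, with SD 1 within each order, and let e be the repeat-test effect (second minus first), equal in both orders. Then D has mean (phase effect + e) in early-first women and (phase effect - e) in late-first women. The plain mean of D is shifted by e x (n1 - n2)/34, where n1 is the number early-first and n2 the number late-first. This is exact for the mean difference; the Wilcoxon test moves in the same direction, only approximately in proportion.

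**False-positive rate of the planned paired t-test, no phase effect.** Noncentral t for one shared order; simulation for mixed splits.

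| n1/n2 | shift as multiple of e | e = 0.1 SD | e = 0.2 SD | e = 0.3 SD |
|---|---|---|---|---|
| 17/17 | 0 | 4.9% | 4.6% | 4.2% |
| 20/14 | 6/34 = 0.18 | 5.0% | 5.0% | 5.0% |
| 26/8 | 18/34 = 0.53 | 6.0% | 8.9% | 13.3% |
| 30/4 | 26/34 = 0.76 | 7.1% | 13.6% | 24.3% |
| 34/0 | 1 | 8.8% | 20.5% | 39.7% |

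Masking is the mirror image. With a true effect of 0.5 SD and e = 0.2 SD, power of the planned test falls to about 60% at 8 early-first and 26 late-first, and to 40% if all are late-first.

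**Order-adjusted estimate.** Take the unweighted mean of the two order-specific mean differences: SE = sqrt(0.25 x (1/n1 + 1/n2)), 32 df. With equal effects in both orders the bias is zero and the error rate 5%.

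| n1/n2 | SE | 95% CI half-width (SD) | power at 0.5 |
|---|---|---|---|
| 17/17 | 0.1715 | 0.35 | 0.807 |
| 20/14 | 0.1742 | 0.36 | 0.795 |
| 26/8 | 0.2022 | 0.41 | 0.670 |
| 30/4 | 0.2661 | 0.54 | 0.445 |

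At 34/0 no order effect can be estimated.

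**Limit of the adjustment.** If the effect is e1 in early-first and e2 in late-first women, the adjusted bias is (e1 - e2)/2. For 0.3 against 0 this is 0.15 SD, and the adjusted error is 13.6% at 17/17 (unadjusted 13.0%) and 11.1% at 26/8.

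Unequal effects are plausible because the interval depends on order. Protocol section 1 gives "early follicular (days 1-5), late follicular (days 6-12") and ends the cycle at "late luteal phases (24-28 days"). With L days of bleeding, the early test is on cycle day 3 and the late test on day L + 3. Bleeding on day 3 needs L of at least 3; a late test by day 12 needs L of at most 9. In a 28-day cycle, early-first gives an interval of L = 3-9 days if both tests fall in one cycle, or 28 + L = 31-37 days if the late test falls in the next. Late-first gives 28 - L = 19-25 days.

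**The case against.** The strongest objection is that the order may be drawn in the study-flow figure. That stands: a reader might infer that the plan has no order rule, but the documents support only that the readable text states none. The figure would not settle the matter by itself. A fixed early-then-late order gives the full shift and leaves no way to estimate an order term, while a balanced order would still need stating in the SAP.

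Second, no harm is demonstrated. The documents contain no evidence of a repeat-test effect on the ST/HR index and no split. A reader might take 40% as the study's false-positive rate; it needs the largest assumed effect and one shared order together. Near balance the planned test is sound on this point.

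Third, a reader might use exclusion criterion 10 as evidence of bias in the primary endpoint, because it acts on the first test only. By regression to the mean it could favour first-test exercise capacity (METs), a secondary endpoint. Nothing in the documents links it to the ST/HR index, and they give no intolerance rate.

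Fourth, adjustment is imperfect. If the repeat-test effect occurs only in late-first women (0.3 SD against 0), adjustment at 20/14 gives 13.3% error against 10.4% unadjusted; if only in early-first women, 13.3% against 16.5%. This supports reporting both analyses with the assumption stated, rather than replacing the planned test.

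Fifth, balancing may be impractical for a clinically ordered test, and the protocol dates recruitment to February-July 2023. The request to balance is therefore conditional; deriving and reporting order is not.

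**Conclusion.** The point holds in conditional form: the readable text allows either phase first, the analysis has no order term, and any repeat-test effect shifts the ST/HR index difference by that effect times (n1 - n2)/34. The error rates in the table rest on assumed effects of 0.1-0.3 SD, equal in both orders, and on assumed splits. Severity is minor to moderate: nothing is lost at balance, but at 26/8 or beyond the planned test alone could mislead, and with one shared order phase and order cannot be separated.

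A reader might also treat the telephone contact between the tests ("Phone visit on day 7 after ETT (± 2 days")) as part of this problem. With L = 3-4 a same-cycle second test would precede the day 5-9 window, so those passages need reconciling, but that is a separate scheduling matter and says nothing about order bias.

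**What to change.** 1. State in the protocol text and the SAP which phase is tested first or how that is decided, and whether both tests fall in one cycle.
2. Where scheduling of the clinically ordered test allows, balance the starting phase at about 17/17.
3. Derive order and interval from the two ETT dates; report the split, and the interval by order.
4. Next to the planned paired test, and whatever the split, pre-specify an order-adjusted phase difference with its 95% CI for the ST/HR index and the other exercise-test and troponin endpoints: phase and test order as fixed effects, woman as random effect. If the differences are skewed, compare second-minus-first differences between order groups by rank-sum test. State the assumption of an equal repeat-test effect in both orders.
5. Do not claim a phase effect in the ST/HR index unless the order-adjusted estimate supports it, and define that support in advance. If all women share one order, say that phase and order cannot be separated and limit the conclusion.

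**Cost.** No added tests. Power falls from 0.808 to 0.807 at 17/17 and 0.795 at 20/14. When unbalanced the loss is real: 0.670 at 26/8 and 0.445 at 30/4, with wide intervals; 80% adjusted power would need about 46 women at a 26:8 ratio and 78 at 30:4. Moving a woman from early-first to late-first puts her clinically ordered test about L = 3-9 days later, which is why balancing is conditional. Neither balance nor adjustment removes bias if the repeat-test effect depends on the interval.
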